Atrial fibrillation (AF) represents the most common sustained arrhythmia in western societies. Currently, in Germany, approximately two million patients are affected by AF and are exposed to an increased risk of stroke, heart failure and mortality ¹. AF often coexists with heart failure with preserved ejection fraction (HFpEF)^{2 3}. Due to the co-occurrence of AF and HFpEF in this population many patients require emergency hospitalization. However, diagnosis and optimal therapy of this combined entity remains often uncertain despite of recent developments. Due to the progressive ageing of our society and demographic development, the number of AF patients is expected to double over the next several years ⁴. Moreover, AF has emerged as one of the most common reasons for patients seeking treatment in emergency rooms (ER) who are subsequently admitted for in-hospital treatment ⁵. For many years, it has been well established that second line catheter ablation is more effective than escalation of antiarrhythmic drug treatment (AAD) with regards to rhythm control ⁶. However, technical complexity of AF ablation, safety concerns and lack of reproducibility has limited widespread utilization of the former gold standard of radiofrequency current (RF) energy ablation. Importantly, the globally-performed CABANA trial failed to demonstrate reduction of mortality, but confirmed a lower AF burden following ablation therapy ⁷. Recently, the randomized EAST strategy trial comparing rhythm control (achievement of sinus rhythm via intervention) vs. best medical care (rate control medication) demonstrated a 20% reduction of clinical endpoints such as cardiovascular mortality, stroke, embolism in the group randomized to rhythm control ⁸. However, RF catheter ablation was utilized in only 20% of patients. Interestingly, very recently three independent randomized trials compared first line single shot PVI (Cryoballoon) vs. AAD treatment in more than 700 patients ^{9, 10, 11}. Importantly, the findings were uniformly showing increased efficacy for first line ablation using single shot device. The Farapulse electroporation device has demonstrated its ease in use, very short procedure times and a high procedural safety even in complex anatomy ^{12 13}. **Catheter ablation using electroporation (non-thermal energy source) differs substantially from thermal energy sources such as Cryo or RF energy and demonstrated a favorable safety profile. (Ekanem et al. Europace 2022).** Thus, the concept of an early rhythm control strategy using a safe and reproducible single-shot ablation technology, such as electroporation, appears to be suitable to investigate the role of a stringent rhythm control in AF patients with HFpEF vs. usual care after emergency hospitalization.

4. Methods

Symptomatic paroxysmal AF patients diagnosed with HFpEF seeking emergency treatment that meet all inclusion and none of the exclusion criteria will be randomized according to E-TEAM in two groups (1:1 randomization) as follows:

Group 1: early catheter ablation within 7 days post AF-related emergency treatment using the FARAPULSE electroporation technology (n = 100)

OR

Group 2: best medical AF treatment including rhythm and rate control (n=100)

All patients will receive (direct) oral anticoagulation and heart failure treatment according to their CHA₂DS₂-VASC Score and current ESC guidelines ^{1 2}.

5. Ablation

The FARAPULSE AF ablation system represents a unique single shot ablation technology associated with a high rate of acute and durable PV isolation ¹⁴. In principle, electroporation delivers a cardiac selective ablation, thus sparing non-cardiac tissue. The endpoint of the catheter ablation procedure is defined to PVI. Therefore, this technology offers a unique beneficial profile combining a high procedural efficacy and safety.

6. Endpoints

The **primary endpoint** is a composite of cardiovascular hospitalization (worsening heart failure, acute coronary syndrome, AF/AT recurrence, cardioversions, re-ablations), death, systemic embolism, stroke (ischemic, hemorrhagic) and emergency (E) treatment for cardiovascular reasons.

Secondary endpoints are defined to safety parameters such peri-procedural complications (major bleeding requiring intervention, phrenic nerve palsy, pericardial tamponade, thromboembolic events, atrio-esophageal fistula, death) or discontinuation of AAD due to side effects and documented recurrence of AF or any atrial tachyarrhythmia lasting longer than 30 seconds between day 90 and 365 after the index procedure as well as number of nights spent in the hospital per year.

Study Design

The proposed pilot study is a prospective, randomized, single-center feasibility study, enrolling 200 patients with symptomatic paroxysmal AF. Per protocol, 100 patients will undergo a FARAPULSE electroporation PVI and 100 patients will receive standard AF medical treatment.

Prior enrollment, all patients will be informed on the risk and benefits of the PVI procedure as well as the medical treatment. In addition, particular information on the rationale of the study, including a detailed risk/benefit analysis, will be provided to all patients.

After obtaining written informed consent and randomization, patients will be treated according to the assigned groups (FARAPULSE electroporation PVI vs. optimized medical care). Follow-Up duration is 12 months. Importantly, cross-over between both groups is strongly discouraged. **If deterioration occurs in group 2, PVI is advised.**

Risk-Benefit-Analysis

Catheter ablation of paroxysmal AF represents an invasive procedure but is linked to a lower AF recurrence rate if compared to medical treatment. Participants in Group 2 (control group) will receive best medical treatment including the option for electrical cardioversions and AAD treatment.

The novel energy source using electroporation appears to be appealing due to its potential of short procedure times and cardiomyocyte selectivity resulting in a benign safety profile. The participants in Group 1 will be scheduled to receive the ablation therapy early after the AF diagnosis (within 7 days).

In general, catheter ablation for AF is an invasive treatment associated with potential complications. Of note, as stated above electroporation appears to be associated with a very benign risk profile. General AF related complications and corresponding incidences are summarized in the following:

- Vascular access complications such as vascular damage, neural damage, hematoma, bleeding (approx. 2-3%)
- Pericardial tamponade (<1%)
- Systemic Infection (<1%)
- Thrombo-embolic complications including air embolism, transient ischemic attack and stroke (<1%)
- Pulmonary vein stenosis or occlusion (<0,5%)
- Atrio-esophageal fistula (< 1%)
- Death (< 0.1%)

All devices utilized for the ablation procedure are fully licensed, CE mark approved and are used in the clinical routine. Patients randomized to Group 2 will receive standard medication including all non-interventional options for a rhythm control strategy in the treatment of paroxysmal AF. Therefore, no patient will be exposed to a higher risk due to the participation in the E-TEAM-Trial.

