6.2 Study course

6.2.1 Visit 1, Pre-procedural, Day -2 to 0

Following emergency hospital admission diagnostic work up including physical examination, 12 lead ECG, emergency blood examination (NT-proBNP) and chest X-ray initial cardiac ultrasound. Initiation and optimization of emergency therapy including iv diuretics if required. Routine diagnostic work up during hospital stay including daily clinical evaluation, weight loss determination, complete cardiac ultrasound, 12 lead ECG, telemetry, routine blood examination (30 ml) for blood cell count, INR, creatinine, ALAT, ASAT, electrolytes, TSH, NT-proBNP according to clinical needs.

Randomization (1:1) will be performed by the E-TEAM after all the patients' questions were clarified and the ICF was signed. All patients randomized to Group 1 will proceed to preparation of Visit 2, pulmonary vein isolation. The patients randomized in Group 2 will receive best medical treatment and if rhythm control was attempted TEE guided cardioversion and AAD according to the patients clinical needs as well as all information regarding the medical treatment.

In order to exclude intracardiac thrombi, a transesophageal echocardiogram (TEE) will be performed in patients randomized to Group 1 and considered at risk for thrombus formation and stratified to rhythm control (Group 2, before cardioversion). In case of TEE proven LAA thrombus the scheduled AF ablation or cardioversion can be postponed.

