6.2.3 Visit 3, Hospital Discharge

Until discharge, all patients will be monitored using telemetry and all patients in Group 1 will undergo a repeat TTE to exclude pericardial effusion and a daily 12 lead electrocardiography (ECG) to document the heart rhythm. A blood sample (20 ml) will be routinely collected to exclude bleeding (blood cell count) or renal function deterioration (creatinine and electrolytes). Therapeutic anticoagulation preferentially using a novel oral anticoagulant (NOAC) over Vitamin K antagonist will be initiated or resumed the evening after the procedure and maintained for at least 8 weeks after ablation. Continued anticoagulation will be performed if necessary, according to the individual CHA2DS2-Vasc-Score. In both groups early cardioversions in case of very early recurrence during the index hospital stay are allowed. AAD treatment in Group 1 should be avoided and should be stopped after 3 months, in Group 2 AAD treatment is allowed if rhythm control was selected according to the patients clinical profile. Total nights spent in hospital will be counted.

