6.3 Repeat ablation

No blanking period will be utilized in this study. During the first 90 days after the index procedure any arrhythmia recurrence shall be treated conservatively, e.g. by antiarrhythmic medication and/or ECV. Of note, re-ablation is strongly discouraged within the first 3 months. At day 90 however, all AAD drugs should be stopped in the ablation group and all re-ablation afterwards will meet the primary endpoint. In case of re-ablation the patient has reached the primary endpoint. The Follow-Up visits should be continued as per protocol.

7. Participant withdrawal or termination of participation

Prior to study entry, all participants will be informed that they are free to withdraw from the study at any time and for any reason without prejudice to their future medical care by a physician or the institution. Participants are free to withdraw from participation in the study at any time upon request. The withdrawal will cause no penalty or loss of benefits, to which the patients may otherwise be entitled. The investigator may ask and document the patients' motivation.

An investigator may also terminate a patients' participation in the study if:

- Withdrawal is in the subjects' best interest.
- Subject withdraws consent.
- Subject is lost to follow up.

8. Statistical Analysis

No interim-analysis will be performed.

The following events will trigger a premature study termination:

- Occurrence of serious adverse events in more than 10% of the study population associated with the ablation procedure. Of note, re-hospitalization for cardiovascular reasons meets the primary study endpoint.
- Occurrence of any unexpected, currently unknown complication or risk (Change of Risk-Benefit Ratio).

Occurrence of >10% major procedural complications defined as cardiac tamponade, stroke/TIA, air embolism, major bleeding the study has to be stopped. Of note re-hospitalization for cardiovascular reasons meets the primary endpoint.”

9. Adverse Events

All adverse events (AEs) experienced by participants during the study, beginning with the first study related procedure and continuing through the end of study, will be recorded on case report forms (CRFs). Occurrences of atrial fibrillation and atrial flutter will be recorded and reported on as part of the efficacy assessment, and are not considered adverse events.

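### Cardioversion is a named primary-endpoint component and also part of Group 2's assigned care, and the protocol does not say whether an initial cardioversion, in the index stay or postponed, counts as an event

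*Protocol*

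**What the plan says.** - Section 6, Endpoints: one part of the primary composite is "cardiovascular hospitalization (worsening heart failure, acute coronary syndrome, AF/AT recurrence, cardioversions, re-ablations", so cardioversion is listed within the hospitalization component. The secondary recurrence endpoint has a window of day 90 to 365; the primary endpoint has none.
- Risk-Benefit-Analysis: Group 2 receives "best medical treatment including the option for electrical cardioversions and AAD treatment".
- Section 6.2.1, after randomization: Group 2 receives best medical treatment and, "if rhythm control was attempted TEE guided cardioversion and AAD according to the patients clinical needs". The same section adds: "In case of TEE proven LAA thrombus the scheduled AF ablation or cardioversion can be postponed".
- Section 6.2.3: "In both groups early cardioversions in case of very early recurrence during the index hospital stay are allowed". It does not say whether these count.
- Section 6.3: "No blanking period will be utilized in this study". In the first 90 days after the index procedure, "any arrhythmia recurrence shall be treated conservatively, e.g. by antiarrhythmic medication and/or ECV". On re-ablation: "In case of re-ablation the patient has reached the primary endpoint".
- Sections 8 and 9 refer three times to re-hospitalization for cardiovascular reasons as meeting, or being part of, the primary endpoint.
- Sections 6.2.4 to 6.2.6 time visits from the procedure in Group 1 and from randomization in Group 2. No section says when counting of primary events starts.

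**The concern.** An endpoint component should record failure of the assigned strategy, not its delivery. In Group 2, a first cardioversion can be the delivery of rhythm control. The equivalent step in Group 1, the index PVI, is not a listed component; only re-ablation is. If initial cardioversions are scored, some control patients reach the primary endpoint by receiving their assigned care, and the comparison tilts towards ablation.

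If they are scored for some patients and not others, the result depends on who reads the definition. Treatment is evident to everyone at the single center, so an unsettled rule is applied with the arm in view. If only the first event is analysed, an early procedural event would also hide later clinical events in the same patient.

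**Working it through.** **Step 1. Does an index-stay cardioversion count?** Two readings fit the text.

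- *Re-hospitalization reading.* The bracket qualifies a hospitalization, and Sections 8 and 9 call it a re-hospitalization. A cardioversion before index discharge is then not an event.
- *Stand-alone reading.* Section 6.3 says that a re-ablated patient has reached the endpoint and mentions no new admission. Cardioversion stands in the same bracket, no section exempts it, and blanking is ruled out. A cardioversion on the ward is then an event.

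The first reading has more text behind it, but the second is not excluded.

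**Step 2. Does a postponed initial cardioversion count?** Section 6.2.1 allows postponement for LAA thrombus. If the procedure is then done at a new admission, that is a cardiovascular hospitalization for cardioversion, and it scores on either reading. A postponed index PVI is not a listed item.

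**Step 3. Size if counted.** The protocol gives no event rate and no cardioversion rate, so there is no stated figure to reproduce. All rates below are assumptions. Let p be the true 12-month risk, equal in both arms, and c the share of Group 2 with a counted initial cardioversion. Take p = 40% and c = 20 to 50%.

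- Cardioversion independent of later events: scored risk = c + (1 − c)p. For c = 20%, 0.20 + 0.80 × 0.40 = 52%, a gap of 12 points. For c = 50%, 0.50 + 0.50 × 0.40 = 70%, a gap of 30 points.
- Complete overlap (cardioverted patients are those who would have had an event anyway, as far as numbers allow): scored risk = max(c, p). For c = 20% this is 40%, a gap of 0. For c = 50% it is 50%, a gap of 10 points.
- Independence, with 10% of Group 1 also scoring: Group 1 = 0.10 + 0.90 × 0.40 = 46%, so the gaps are 52 − 46 = 6 and 70 − 46 = 24 points.

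For the postponed route alone, with 100 patients per group, each Group 2 patient who scores this way and is otherwise event-free adds 1/100 = 1 point.

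**Step 4. Chance of a false significant result favouring ablation.** This assumes independence, 100 per group, a two-sided 5% level and a normal-approximation comparison of two proportions. Scored risk = 1 − (1 − p)(1 − c).

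| p | Group 1 counted | Group 2 counted (c) | Scored risks | Chance |
|---|---|---|---|---|
| 30% | 0% | 10% | 30% vs 37% | 18% |
| 30% | 0% | 20% | 30% vs 44% | 54% |
| 30% | 0% | 30% | 30% vs 51% | 86% |
| 20% | 0% | 20% | 20% vs 36% | 72% |
| 40% | 0% | 20% | 40% vs 52% | 40% |
| 30% | 10% | 20% | 37% vs 44% | 17% |
| 30% | 10% | 30% | 37% vs 51% | 51% |

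If initial cardioversions are excluded in both groups, the spurious gap in this illustration is zero.

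**The case against.** The strongest reply is that the protocol counts hospitalizations, not procedures, and says re-hospitalization three times. A patient cardioverted on the ward before discharge has not been re-hospitalized. The re-ablation sentence follows one about re-ablation after day 90, long after the index stay, so it fits that reading too. The statement on blanking stands in the section on repeat ablation and does not turn index-stay treatment into an event. This largely stands: a reader might infer that, taken literally, every ward cardioversion in Group 2 is a primary event, and the text does not support that.

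A reader might also infer that the whole control arm is exposed. It is not. Cardioversion is conditional on rhythm control being attempted, rate control is an alternative, all patients have paroxysmal AF, and Group 1 may also be cardioverted during the index stay. Nor can a fixed bias of 12 to 30 points be claimed, since that range needs assumed rates, independence and the stand-alone reading all at once.

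An analysis plan, not shown here, might settle the counting. But the protocol itself defines the endpoint, rules out blanking and scores re-ablation, so the rule belongs there. The objection also does not reach the postponed cardioversion, which scores under the re-hospitalization reading itself.

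**Conclusion.** The point holds as an unsettled counting rule in the primary endpoint, with one route by which assigned control care is scored as failure on either reading. It does not hold as a plain rule that control patients score by being treated.

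Where initial cardioversions are counted, the bias favours ablation. Its size cannot be derived from the protocol. With p = 40% and c = 20 to 50%, both assumed, it lies between about 0 points (complete overlap) and 30 points (independence, none counted in Group 1). For index-stay cardioversions it is zero on the re-hospitalization reading. Only the postponed procedures then remain, and the protocol gives no frequency for them. Severity: should fix.

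**What to change.** Add a counting rule to Section 6, Endpoints, with a cross-reference in Section 6.3:

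- Primary events count from randomization in both groups.
- Not counted in either group: a cardioversion during the index hospital stay, including during the index PVI; the first cardioversion planned at the index stay as part of assigned treatment, even if postponed to a later admission; and an admission solely to deliver a postponed index PVI.
- Counted in both groups: any later hospitalization for cardioversion of recurrent AF/AT.

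Then reconcile Sections 6.2.1, 6.2.3, 6.3, 8 and 9 with this rule. A simpler rule that counts every cardioversion after index discharge would not do: it would lock in the postponed-procedure bias and drop the hospitalization requirement.

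The cost is a short paragraph, plus CRF items for the date of each cardioversion and whether it was the initial planned one. No patient's treatment changes. The downside is that a true very early relapse cardioverted before discharge goes unscored, in both arms alike.

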Serious adverse events (SAEs) are events that place the participants health in jeopardy and that occur despite following all labeling precautions and instructions for use and where all attempts at correction by medical intervention do not resolve the event. All SAEs must be reported to the Ethics Committee (EC) within 48 hours of the investigator becoming aware of the SAE. Re-hospitalization for cardiovascular reasons is part of the primary endpoint and therefore does not qualify as an SAE.

An unanticipated adverse device effect (UADE) is defined as any SAE on health or safety, or any life-threatening problem or death caused by, or associated with, the device, if that effect, problem, or death was not previously identified in nature, severity, or degree of incidence in the investigational plan or application. An UADE is also defined as any other unanticipated serious problem associated with a device that relates to the rights, safety, or welfare of participants.

Should an UADE occur, the investigator is required to notify the EC as soon as possible, but in no event later than 10 working days after the investigator first learns of the event. An immediate evaluation of any UADE will be conducted. If there is significant new information that could affect the risk/benefit analysis as given in Section 7.1 of this protocol, the ECs will be informed and if appropriate, actions such as study hold, patient re-consent or study termination will be taken.

All participant deaths must be immediately reported to the EC (24 h upon investigators knowledge). When possible and permitted by family members, an autopsy shall be performed. The death certificate, coroner's report, and laboratory and autopsy reports, if available, should be provided to the EC.

10. Documentation

All patient data will be documented in CRFs. Personal data such as name, address, contact data etc. are excluded from the documentation in the eCRF. Names of all patients will be pseudomized and underlie national data protection laws. The principal investigator will conserve the patient identification list, the signed informed consent forms and the original data including the patient chart for 15 years.

11. Study organization

Principle Investigators: [name]. med. [name]
MVZ CCB Frankfurt und Main Taunus GbR
Am Agaplesion Markus Krankenhaus
[name]
[contact]
Fax: [name]
E-Mail: [contact]

Priv. Doz. Dr. med. [name]

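### The Risk-Benefit-Analysis concludes that taking part adds no risk for any patient, which its own list of ablation complications contradicts for Group 1

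*Protocol*

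**What the plan says.** The Risk-Benefit-Analysis of the Protocol contains both halves of the problem.

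- On the procedure it says: "In general, catheter ablation for AF is an invasive treatment associated with potential complications". It then lists seven types of complication with incidences. The first is "Vascular access complications such as vascular damage, neural damage, hematoma, bleeding (approx. 2-3" per cent). The others carry upper limits only: tamponade, systemic infection, thrombo-embolism including stroke, and atrio-esophageal fistula each below 1%; pulmonary vein stenosis below 0.5%; death below 0.1%.
- It closes with: "Therefore, no patient will be exposed to a higher risk due to the participation in the E-TEAM-Trial". Two reasons precede this: the ablation devices are CE-marked and in routine use, and Group 2 receives standard medication.

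Three other places bear on the sentence.

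- The introduction frames the comparison as one against usual care, and Study Design assigns 100 patients to ablation and 100 to standard medical treatment.
- Study Design says that information on the rationale of the study, "including a detailed risk/benefit analysis, will be provided to all patients". The sentence before it requires that patients also be told the risks and benefits of both the ablation and the medical treatment.
- Section 9 (Adverse Events) makes possible study hold, re-consent or termination depend on "significant new information that could affect the risk/benefit analysis as given in Section 7.1 of this protocol".

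**The concern.** The conclusion is absolute: it covers every patient, and it speaks of risk, not of the balance of risk and benefit. Neither reason given supports it for Group 1. CE marking and routine use show that the devices are licensed; they do not show that having the procedure adds no risk to a patient who would otherwise be treated medically. The second reason concerns Group 2 only.

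The rest of the Protocol assumes that procedural risk exists. Peri-procedural complications, including death, are a secondary endpoint in section 6, and section 8 stops the study if ablation-related serious events or major procedural complications exceed 10%.

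What is at stake is the accuracy of the risk statement in the analysis that is promised to patients and that section 9 names as the reference for new safety information.

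**Working it through.** The Protocol gives no figure for added risk, so there is nothing to reproduce. The check asks whether a conclusion of no added risk can be squared with the Protocol's own rates.

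**Inputs**

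- Patients allocated to ablation: n = 100 (section 4 and Study Design).
- Vascular access complication rate: p = 0.02 to 0.03 (Risk-Benefit-Analysis).
- All other listed items: upper limits only. They are set to zero here, which is the reading most favourable to the sentence.

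**Step 1. Expected number affected in Group 1, n × p**

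- At 2%: 100 × 0.02 = 2 patients.
- At 3%: 100 × 0.03 = 3 patients.

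**Step 2. Chance of at least one case in Group 1, 1 − (1 − p)^n, patients independent**

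- At 2%: 1 − 0.98^100 = 1 − 0.133 = 0.867.
- At 3%: 1 − 0.97^100 = 1 − 0.048 = 0.952.

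Even with every item marked as below a limit set to zero, vascular complications are therefore expected in the ablation arm.

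**Step 3. Is this risk due to participation?**

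Let f be the share of Group 1 patients who would have had the same early ablation outside the trial. The number affected because of allocation is then (1 − f) × 2 to (1 − f) × 3. It reaches zero only if f = 1. The Protocol does not say that f = 1, and its description of the comparator as usual care points the other way.

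**Step 4. The stated reasons set against the conclusion**

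| Reason given | What it supports | Does it cover Group 1? |
|---|---|---|
| Devices CE-marked, in routine use | Licensing of the devices | Not as to added risk |
| Standard medication in Group 2 | No added treatment risk in Group 2 | No |

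The conclusion may be defensible for Group 2. It is not supported for Group 1.

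**The case against.** The strongest reply is that the sentence is loose wording with little consequence. Several parts of that reply stand.

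- **What patients are told.** A reader might infer that patients are told something untrue. The documents do not show this. The consent text is not available, and Study Design separately requires disclosure of the ablation risks. What can be said is that the analysis to be provided would carry an untrue conclusion unless the patient information words it differently.
- **Later safety reviews.** A reader might infer that these reviews start from a wrong baseline. They need not. Section 9 judges an unanticipated device effect by whether its nature, severity or incidence was already identified, and the itemised list supplies that. The triggers in section 8 rest on unknown complications or on 10% thresholds. None of them uses the closing sentence.
- **A total risk.** It is tempting to add the list: 3 + 1 + 1 + 1 + 0.5 + 1 + 0.1 = 7.6%. This adds ceilings to an approximate range, counts death separately although it overlaps with other items, and uses rates given for ablation in general, while the text expects electroporation to be more benign. It is not an estimate and should not be printed as one.
- **Gross versus excess risk.** Group 2 may receive antiarrhythmic drugs and cardioversion, which have risks of their own. The Protocol gives no harm rates for them, so net excess risk cannot be computed. The figures above are Group 1's gross procedural risk.
- **Group 2.** A reader might infer that Group 2 patients are denied ablation. Cross-over is discouraged, but the next sentence advises PVI if a Group 2 patient deteriorates.

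None of this rescues the sentence. An expected benefit, or unquantified drug risks in the other arm, may make the overall balance favourable. The sentence does not claim a favourable balance; it claims that risk is not raised for anyone.

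**Conclusion.** The closing sentence of the Risk-Benefit-Analysis is wrong as written for Group 1. On the Protocol's own figures, vascular access complications alone imply 2 to 3 affected patients among 100, with an 87% to 95% chance of at least one.

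This rests on three assumptions: the listed general ablation rate applies to this procedure, patients are independent, and Group 1 patients would not all have had the same early ablation outside the trial. The size is a gross procedural risk for one item. It is neither a total nor a net excess over medical treatment.

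Severity is minor to moderate. The risks are itemised just above the sentence, their disclosure is required elsewhere, and no endpoint, analysis or stopping threshold depends on it. It still merits correction because it stands in the analysis promised to all patients and cited in section 9. The reference there to a Section 7.1 is a separate, editorial matter: section 7 deals with withdrawal, and no 7.1 appears in the text shown.

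**What to change.** 1. Replace the closing sentence with a statement that allocation to Group 1 adds the procedural risks already listed, at the rates already listed and without a summed total. Say that these are weighed against the expected benefit and against the risks of medical treatment in Group 2.
2. Check that the patient information says the same, and amend it if it repeats the sentence.
3. Correct the Section 7.1 reference in section 9 so that it points to the Risk-Benefit-Analysis.

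The cost is a wording amendment and, if needed, an updated patient information sheet. The stated risk becomes less favourable. No procedure, endpoint or stopping threshold changes.
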